10.3.2. Potential Hy's Law Cases

Sites must report every participant who meets the following potential Hy's law criteria if this occurs within the time the participant signs the ICF until 30 days after the last dose of study intervention:

- ALT or AST $\geq 3 \times$ ULN **AND**
- Total bilirubin $\geq 2 \times$ ULN **AND**
- Alkaline phosphatase $< 2 \times$ ULN

Study site personnel must report every participant who meets these criteria. Typically, all 3 analytes will be obtained from the same sample, but they may come from multiple samples taken within a 24-hour period. This requirement applies from the time the participant signs the ICF for the study until 30 days after the final protocol-defined study visit or the last known dose of study intervention (if the final visit does not occur). A laboratory alert for possible

Hy's law cases will be in place, to notify investigators and the sponsor immediately when the above criteria have been met. A possible Hy's law case must be faxed by the investigator to the sponsor on an abnormal liver function reporting form as soon as possible (within 24 hours of learning of the possible Hy's law case) to the fax number on the form or the SAE fax number, even if no AE has occurred. If the event is serious, please complete the SAE form. The eCRF for possible Hy's law cases must be completed within 7 calendar days. Every effort to determine the cause of the liver enzyme abnormalities must be made, and close monitoring should be initiated in conjunction with the medical monitor and medical safety physician and in accordance with the FDA Guidance for Industry, Drug-Induced Liver Injury: Premarketing Clinical Evaluation, July 2009. The participant should return to the study site and be evaluated as soon as possible, preferably within 48 hours from the time the investigator becomes aware of the abnormal results. This evaluation should include laboratory tests, detailed history, and physical assessment.

Events Meeting the AE Definition

- Any abnormal laboratory test results (hematology, clinical chemistry, or urinalysis) or other safety assessments (eg, ECGs, radiological scans, vital signs measurements), including those that worsen from baseline, considered clinically significant in the medical and scientific judgment of the investigator (ie, not related to progression of underlying disease); for example:
 - The test result is associated with accompanying symptoms, and/or
 - The test result requires additional diagnostic testing or medical/surgical intervention, and/or
 - The test result leads to a change in study dosing (outside of any protocol-specified dose adjustments) or discontinuation from the study, significant additional concomitant drug treatment, or other therapy, and/or
 - The test result is considered to be an AE by the investigator or sponsor.
- Exacerbation of a chronic or intermittent pre-existing condition including either an increase in frequency and/or intensity of the condition
- New condition detected or diagnosed after study intervention administration even though it may have been present before the start of the study
- Signs, symptoms, or the clinical sequelae of a suspected drug-drug interaction
- Signs, symptoms, or the clinical sequelae of a suspected overdose of either study intervention or a concomitant medication. Overdose per se will not be reported as an AE or SAE unless it is an intentional overdose taken with possible suicidal/ self-harming intent. Such overdoses should be reported regardless of sequelae.
- Lack of efficacy or failure of expected pharmacological action per se will not be reported as an AE or SAE. Such instances will be captured in the efficacy assessments. However, the signs, symptoms, and/or clinical sequelae resulting from lack of efficacy will be reported as AEs or SAEs if they fulfil the definition of an AE or SAE.

Events NOT Meeting the AE Definition

 • Any clinically significant abnormal laboratory findings or other abnormal safety assessments that are associated with the underlying disease, unless judged by the investigator to be more severe than expected for the participant’s condition. Merely repeating an abnormal test, in the absence of any of the above conditions, does not constitute an AE. Any abnormal test result that is determined to be an error does not require recording as an AE. • The disease/disorder being studied or expected progression, signs, or symptoms (clearly defined) of the disease/disorder being studied, unless more severe than expected for the participant’s condition • The following events are considered to be manifestations of migraine and will be captured in the eDiary as symptoms of the disease but they will not be reported as AEs, unless they change in severity or frequency warranting an AE, or meet criteria of SAE: 
 • Signs and symptoms associated with acute migraine attack, eg, aura symptoms, headache pain, nausea and vomiting, sensitivity to light or sound. 
If the investigator considers these manifestations to have a reasonable possibility of relationship to the study intervention(s), then they should be reported as AEs or SAEs, respectively.
 • Medical or surgical procedure (eg, endoscopy, appendectomy): the condition that leads to the procedure is the AE • Situations in which an untoward medical occurrence did not occur (social and/or convenience admission to a hospital) • Anticipated day-to-day fluctuations of pre-existing disease(s) or condition(s) present or detected at the start of the study that do not worsen

Definition of SAE

SAEs must meet both the AE criteria described above and the seriousness criteria listed below.

An SAE is defined as any untoward medical occurrence that, at any dose:

a. Results in death

b. Is life threatening
 
The term life threatening in the definition of serious refers to an event in which the participant was at risk of death at the time of the event. It does not refer to an event that hypothetically might have caused death if it were more severe.

c. Requires inpatient hospitalization or prolongation of existing hospitalization

In general, hospitalization signifies that the participant has been detained (usually involving at least an overnight stay) at the hospital or emergency ward for observation and/or intervention that would not have been appropriate in the physician's office or outpatient setting.

Complications that occur during hospitalization are AEs. If a complication prolongs hospitalization or fulfills any other serious criteria, the event is serious. When in doubt as to whether hospitalization occurred or was necessary, the AE should be considered serious.

Hospitalization for elective intervention of a pre-existing condition that did not worsen from baseline is not considered an AE.

d. Results in persistent disability/incapacity

- The term disability means a substantial disruption of a person's ability to conduct normal life functions.
- This definition is not intended to include experiences of relatively minor medical significance such as uncomplicated headache, nausea, vomiting, diarrhea, influenza, and accidental trauma (eg, sprained ankle), which may interfere with or prevent everyday life functions but do not constitute a substantial disruption.

e. Is a congenital anomaly/birth defect

f. Other situations:

- Medical or scientific judgment should be exercised in deciding whether SAE reporting is appropriate in other situations such as important medical events that may not be immediately life threatening or result in death or hospitalization but may jeopardize the participant or may require medical or surgical intervention to prevent one of the other outcomes listed in the above definition. These events should usually be considered serious.

Examples of such events include invasive or malignant cancers, intensive intervention in an emergency room or at home for allergic bronchospasm, blood dyscrasias or convulsions that do not result in hospitalization, or development of drug dependency or drug abuse.

Recording and Follow-up of AEs and/or SAEs

AE and SAE Recording	

 • When an AE or SAE occurs, it is the responsibility of the investigator to review all documentation (eg, hospital progress notes, laboratory reports, and diagnostics reports) related to the event. • The investigator will then record all relevant AE or SAE information in the participant’s medical records, in accordance with the investigator’s normal clinical practice and on the appropriate form of the eCRF. • It is not acceptable for the investigator to send photocopies of the participant’s medical records to the sponsor or designee in lieu of completion of the sponsor or designee AE or SAE eCRF page. • There may be instances when copies of medical records for certain cases are requested by the sponsor or designee. In this case, all participant identifiers, with the exception of the participant number, will be redacted on the copies of the medical records before submission to the sponsor or designee. • The investigator will attempt to establish a diagnosis of the event based on signs, symptoms, and/or other clinical information. Whenever possible, the diagnosis (not the individual signs/symptoms) will be documented as the AE/SAE. 	
Assessment of Intensity	
MILD	A type of adverse event that is usually transient and may require only minimal treatment or therapeutic intervention. The event does not generally interfere with usual activities of daily living.
MODERATE	A type of adverse event that is usually alleviated with additional specific therapeutic intervention. The event interferes with usual activities of daily living, causing discomfort but poses no significant or permanent risk of harm to the research participant.
SEVERE	A type of adverse event that interrupts usual activities of daily living, or significantly affects clinical status, or may require intensive therapeutic intervention.

An event is defined as serious when it meets at least one of the predefined outcomes as described in the definition of an SAE NOT when it is rated as severe.
	

Assessment of Causality

- The investigator is obligated to assess the relationship between study intervention and each occurrence of each AE or SAE.
- A *reasonable possibility* of a relationship conveys that there are facts, evidence, and/or arguments to suggest a causal relationship, rather than a relationship cannot be ruled out.
- The investigator will use clinical judgment to determine the relationship.
- Alternative causes, such as underlying disease(s), concomitant therapy, and other risk factors, as well as the temporal relationship of the event to study intervention administration will be considered and investigated.
- The investigator will also consult the investigator brochure in his/her assessment.
- For each AE or SAE, the investigator **must** document in the medical notes that he/she has reviewed the AE or SAE and has provided an assessment of causality. In evaluating causality, the investigator will need to make a Yes/No assessment (ie, related or not related) regarding a reasonable possibility that the study intervention caused the event.
- There may be situations in which an SAE has occurred and the investigator has minimal information to include in the initial report to sponsor or designee. However, **it is very important that the investigator always make an assessment of causality for every event before the initial transmission of the SAE data to the sponsor or designee.**
- The investigator may change his/her opinion of causality in light of follow-up information and send an SAE follow-up report with the updated causality assessment.
- The causality assessment is one of the criteria used when determining regulatory reporting requirements.

Follow-up of AEs and SAEs

- See Section 8.3.3.

Reporting of SAEs

SAE Reporting within 24 hours

 • Email is the preferred method to transmit SAE information. The email address is [contact]. • Facsimile transmission of the SAE information is also acceptable. The fax number is [contact] (backup number is [contact]). • In rare circumstances and in the absence of facsimile equipment, notification by telephone (see the study contact list) is acceptable with a copy of the SAE form, sent by overnight mail or courier service. • Initial notification via telephone does not replace the need for the investigator to complete and sign the SAE form within the designated reporting time frames. • Contacts for SAE reporting can be found on the protocol title page.

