8.3. Adverse Events and Serious Adverse Events

The definitions of an AE or SAE can be found in Section 10.3 (Appendix 3).

AEs will be reported by the participant (or, when appropriate, by a caregiver, surrogate, or the participant's legally authorized representative).

The investigator and any qualified designees are responsible for detecting, documenting, and recording events that meet the definition of an AE or SAE and remain responsible for following up AEs that are serious, considered related to the study intervention or study procedures, or that caused the participant to discontinue the study (see Section 7).

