8.3.1. Time Period and Frequency for Collecting AE and SAE Information

All AEs and SAEs from the signing of the ICF must be collected until 30 days after the last dose of study, regardless of whether or not the participant has been administered study intervention, until the Follow-up Visit (Visit 8) (Section 1.3) and as observed or reported spontaneously by study participants.

Medical occurrences that begin before the start of study intervention, but after obtaining informed consent will be recorded in the AE section of the eCRF and will be considered pretreatment AEs.

All SAEs will be recorded and reported to the sponsor or designee within 24 hours, as indicated in Section 10.3 (Appendix 3). The investigator will submit any updated SAE data to the sponsor within 24 hours of it being available.

Investigators are not obligated to actively seek AE or SAE information after conclusion of the study participation. However, if the investigator learns of any SAE, including a death, at any time after a participant has been discharged from the study, and he/she considers the event to be reasonably related to the study intervention or study participation, the investigator must promptly notify the sponsor.

The method of recording, evaluating, and assessing causality of AEs and SAEs and the procedures for completing and transmitting SAE reports are provided in Section 10.3 (Appendix 3).

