8.3.4. Regulatory Reporting Requirements for SAEs

- Prompt notification by the investigator to the sponsor of an SAE is essential so that legal obligations and ethical responsibilities towards the safety of participants and the safety of a study intervention under clinical investigation are met.
- The sponsor has a legal responsibility to notify both the local regulatory authority and other regulatory agencies about the safety of a study intervention under clinical investigation. The sponsor will comply with country-specific regulatory requirements relating to safety reporting to the regulatory authority, IRBs/IECs, and investigators.

- An investigator who receives an investigator safety report describing an SAE or other specific safety information (eg, summary or listing of SAEs) from the sponsor will review and then file it along with the investigator's brochure and will notify the IRB/IEC, if appropriate according to local requirements.
- Investigator safety reports must be prepared for SUSARs according to local regulatory requirements and sponsor policy and forwarded to investigators as necessary.

8.3.5. Adverse Reactions, Serious Adverse Reactions, and Suspected Unexpected Serious Adverse Reactions – Expedited reporting within the EU

For the purposes of expedited reporting within the EU, the Sponsor will follow the applicable definitions for ARs, SARs, and SUSARs (for example, as outlined in Article 2 [n,o,p] of Directive 2001/20/EC). Also, seriousness criteria for AEs/ARs (as would apply to SARs and SUSARs) are currently included in the protocol, listed in Section 10.3, Appendix 3.

Adverse Reaction: all untoward and unintended responses to an investigational medicinal product related to any dose administered.

Serious Adverse Reaction: an adverse reaction that results in death, is life-threatening, requires hospitalisation or prolongation of existing hospitalisation, results in persistent or significant disability or incapacity, or is a congenital anomaly or birth defect (see Section 10.3, Appendix 3 for further details pertaining to seriousness criteria).

Suspected Unexpected Serious Adverse Reaction: a serious adverse reaction, the nature or severity of which is not consistent with the applicable product information (eg, the investigator's brochure).

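### The SAE definition that sites use counts only persistent disability, while Section 8.3.5 also counts significant disability, so a temporary disabling reaction is left to investigator judgement

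*Protocol*

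**What the plan says.** Section 8.3 of the protocol sends investigators to Section 10.3 (Appendix 3) for the definitions of AE and SAE. In that appendix the disability criterion reads "d. Results in persistent disability/incapacity". Two bullets beneath it explain how large the loss of function must be and exclude minor experiences. The same appendix says that an event is serious "when it meets at least one of the predefined outcomes as described in the definition of an SAE", and that a rating of severe does not make it so. Section 8.3.1 attaches the reporting duty to that status: "All SAEs will be recorded and reported to the sponsor or designee within 24 hours".

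Section 8.3.5, on expedited reporting within the EU, gives its own list for a serious adverse reaction. There the disability limb is a reaction that "results in persistent or significant disability or incapacity". The same section states that "seriousness criteria for AEs/ARs (as would apply to SARs and SUSARs) are currently included in the protocol, listed in Section 10.3, Appendix 3", so the two lists are meant to be one.

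Appendix 3 alone also spells out a criterion f, which leaves other important medical events to medical or scientific judgement and says that such events should usually be treated as serious.

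**The concern.** Both definitions are current protocol text, and they differ by the word *significant*. The narrower one is the one that sites apply. If an investigator reads criterion d literally, a disabling reaction that resolves can be entered as an ordinary AE even though Section 8.3.5 would call it serious.

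Three things depend on that classification: the 24-hour report from site to sponsor, the sponsor's assessment of whether a reaction is a SUSAR, and the treatment-emergent SAE summaries (protocol Section 9.4.2.1; SAP Section 10.2.4), which count only TEAEs that meet an SAE criterion. A definition that drives safety reporting should not give two answers for the same event.

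**Working it through.** No arithmetic applies: the plan states no figure on this point. The check is to take one event through both definitions.

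**Test event.** A drug-related disability that substantially disrupts normal functioning and then resolves, with no death, no threat to life, no admission and no birth defect. The documents do not define *significant*; I assume that a substantial disruption is significant.

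1. **Section 8.3.5.** The disability limb needs persistence *or* significance. The event meets the second, so it is a serious adverse reaction by definition.
2. **Appendix 3, criteria a, b, c and e** (death, threat to life, hospitalization, congenital anomaly). Not met, by construction.
3. **Appendix 3, criterion d.** The bullets settle extent: the disruption must be substantial, and minor complaints are out. The event passes that test. They say nothing that removes *persistent* from the criterion itself, so the event fails on duration.
4. **Appendix 3, criterion f.** It has two limbs. One covers events that may require intervention to prevent another listed outcome; for disability, that outcome is again the persistent kind in criterion d. The other covers events that may put the participant in jeopardy, which is open to judgement. None of the examples is a temporary disability as such, although convulsions without admission come close. The event is serious here only if the investigator decides that criterion f applies.
5. **Other 24-hour routes.** AEs of special interest must also be reported within 24 hours (Section 10.3.1), but that list holds only suicidality, ALT or AST elevations and potential Hy's law cases. It gives no back-up for a disabling event.
6. **Migraine manifestations.** Under Section 8.3.7, aura and other attack symptoms that the investigator considers possibly drug-related are to be reported as AEs or SAEs. Which of the two depends on the same seriousness wording.

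**Result.** The event is serious by definition in Section 8.3.5 and serious by discretion in Appendix 3. Two sites could follow the appendix in good faith and classify it differently.

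**The case against.** The strongest reply is criterion f. It is disjunctive, its default is that such events are usually serious, and its example of convulsions without admission shows that a short-lived neurological event managed outside hospital can qualify. Criterion c takes any case that is admitted. This stands, and it limits the consequence.

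A reader might infer that the event is not an SAE at the site at all, gets no 24-hour report, cannot be assessed as a SUSAR and is hidden from safety review. The documents do not support that. Criterion f can capture it. Section 8 tells sites to raise immediate safety concerns with the sponsor at once. The DSMB reviews unblinded safety data, not stated to be confined to SAEs. The SAP tabulates TEAEs by severity and lists all AEs (Sections 10.2.3 and 10.2.4).

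Scope is also narrow. Section 8.3.5 concerns drug-related reactions and the sponsor's expedited reporting in the EU, so the direct conflict does not extend to unrelated events.

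Finally, the exclusion under criterion d turns on extent and names mostly short-lived complaints; a strict persistence test would make it largely unnecessary. That suggests a drafting slip, not a deliberate narrowing. It may explain how the gap arose, but sites still apply the criterion as written, so the inconsistency remains.

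**Conclusion.** The inconsistency is real and should be corrected. It affects a narrow class: drug-related, substantial, temporary disability without admission or any other listed outcome. For that class, seriousness depends on whether the investigator invokes criterion f. The event may therefore miss 24-hour reporting, timely SUSAR assessment and the treatment-emergent SAE tables. It is not necessarily lost, and it would still appear as an AE.

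No magnitude can be given, because the documents contain no SAE rate. One event in a planned arm of 150 is 1/150, about 0.7 percentage points, but that is the weight of any single event and not a forecast. No efficacy endpoint is affected. The conclusion assumes that *significant* in Section 8.3.5 covers a substantial but temporary loss of function, and that sites classify from Appendix 3, as Section 8.3 directs.

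**What to change.** Reconcile the two passages so that one seriousness wording applies throughout. The direct way is to widen criterion d of Appendix 3 to match the protocol's own Section 8.3.5, so that it covers disability or incapacity that is either persistent or significant. Keep the existing exclusion of minor experiences under criterion d, which limits over-reporting. Any SAE form or training text that repeats criterion d should be checked against the new wording; those materials are not among the documents.

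The cost is two words in the appendix, and possibly some additional events needing expedited handling; the documents do not allow their number to be estimated. The wider wording removes no event now captured. One side effect needs a sentence of text. Section 8.3.7 and Appendix 3 exempt migraine manifestations from AE reporting unless, among other things, they meet SAE criteria, so a wider criterion d could prompt the question whether an ordinary disabling attack now qualifies. The amendment should confirm that the migraine-manifestation rules still apply and say how they interact with the revised criterion.
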